This randomized controlled trial will be conducted in real-world mental health settings providing services to clients within the Massachusetts Department of Mental Health (DMH) community-based system of care, the Mental Health Center of Greater Manchester (MHCGM) in Manchester, NH, the Greater Nashua Mental Health Center of Community Council (GNMHCCC) in Nashua, New Hampshire, and the Community Mental Health Affiliates (CMHA) in New Britain, CT. A total of 144 young adults with SMI and overweight/obesity (BMI ≥ 25) will be recruited from the MHCGM, GNMHCCC, and CMHA, as well as from sites within DMH to participate in a randomized controlled trial. The study will be referred to as the “Fit Forward Lifestyle Trial for in Young Adults.” Participants will be randomized 1:1 to PeerFIT or to Basic Education in fitness and nutrition supported by a wearable Activity Tracking device (BEAT), resulting in approximately 72 clients randomized to PeerFIT and 72 clients randomized to BEAT. Recruitment will occur on a rolling basis with the PeerFIT group intervention starting once at least 2 new people have been randomized to PeerFIT. Thus, we will run open PeerFIT groups in which up to 18 new members are welcome to join at any time during the life of the group. The BEAT individual intervention will begin as soon as 2 participants are randomized to that intervention. This rolling recruitment process combined with open PeerFIT groups is an adaptation to the study design intended to reduce the participant burden of waiting to start the intervention until a full cohort of participants is recruited, which typically takes many months.

INTERVENTION AND CONTROL CONDITION

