3.6.5 Analyses for Study Aims and Hypotheses

Specific Aim 1 (Effectiveness): Mixed effects models will be fit to longitudinal weight, BMI, and cardiorespiratory fitness data. Models will include fixed effects for treatment arm, time and an interaction between treatment arm and time. Additionally, random individual-level intercept and slope terms will be included to account for individual variation in trajectory and simultaneously account for repeated observations within individual. A significant treatment effect of PeerFIT would be indicated by a significant time by treatment interaction accompanied by a mean reduction in weight or BMI or increase in fitness in the PeerFIT group that exceeds the reduction or improvement in the BEAT group (H1a). Similar, non-linear mixed effects models (i.e., longitudinal logistic models) will be fit to the binary cardiovascular risk reduction outcome data (H1b).

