Power Analysis for Aim 1. Assuming a range of within-person, across time correlations (0.1-0.7), with 144 participants (72 per arm), there will be 80% power, at the two-sided 0.05 significance level, to detect a difference between arms in slope of at least 0.030-0.052 SD units per month, or equivalently, 0.36-0.62 SD units over 12 months. If SDs of weight, BMI, and 6-MWT are similar to those observed previously (approximate weight SD 60, BMI SD 9, and 6-MWT SD 350) with the InSHAPE intervention and active control, these standardized effect sizes are equivalent to difference between arms of 21.6-36.0 lbs, 3.20-5.40 BMI units, and 6-MWT of 126-210m over 12 months. With attrition, power will be slightly lower, or equivalently, detectable differences slightly larger. To provide information on detectable differences if maximum attrition is experienced we also provide detectable differences assuming data from only 115 participants (80% of proposed sample size). In this case, the detectable difference increases to 0.034-0.059 SD units per month or 0.41-0.70 over 12 months yielding detectable weight of 24.6-42.0 lbs, BMI of 3.69-6.30, and 6-MWT of 143-245m over 12 months. True power/detectable difference likely lies in between for 144 vs. 115 participants. In the InSHAPE trial, 38% of participants in the active control arm and 51% of participants in InSHAPE achieved a clinically significant change in cardiovascular risk reduction. Because InSHAPE likely had a strong intervention effect with one-on-one personal fitness training and a gym membership for the active control, we estimate that percentages achieving clinically significant change in cardiovascular risk reduction in this study will be 20% for BEAT and 40% for PeerFIT. Assuming these proportions, there will be 86% power to detect a difference between arms in cardiovascular risk reduction, assuming measures of this outcome at 2 time points and within-person correlation of 0.5. With maximum attrition, the power is reduced to 77%.

Specific Aim 2 (Mechanism of Action): To test the mechanism hypotheses, parallel process latent growth curve models will be fit within a structural equation model (SEM) framework. These models allow for testing mediation of the treatment effect on weight and fitness by changes in self-efficacy (H2a) and peer social support (H2b). It is hypothesized that PeerFIT will have a greater effect on the change over time (slope) of

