We expect to enroll and randomize 144 participants in the Fit Forward Lifestyle Trial at study sites within the MA Department of Mental Health, Mental Health Center of Greater Manchester, Greater Nashua Mental Health Center at Community Council, and the Community Mental Health Affiliates. Given our stratified randomization procedure, the intervention allocation should be evenly divided between the experimental and control groups, at approximately 72 each. We chose this sample size because it is sufficient to detect weight loss that has public health significance. The proportion of participants who achieve clinically significant weight loss of $\geq 5\%$ and $\geq 10\%$ will be calculated because modest weight loss contributes to reduction in cardiovascular risk among overweight and obese individuals.

c. Define the target population:

This 12-month randomized controlled trial will recruit 144 young adults ages 18 to 35 with serious mental illness (SMI), defined by a chart DSM-V Axis I diagnosis of a qualifying SMI using diagnostic criteria as defined in the DSM-V for schizophrenia and psychotic disorders, mood disorders, anxiety disorders, and borderline personality disorder. Participants will be recruited from real-world settings providing services to clients within the Massachusetts Department of Mental Health community-based system of care, the Mental Health Center of Greater Manchester, the Greater Nashua Mental Health Center at Community Council, and the Community Mental Health Affiliates.

d. Vulnerable populations

Note: Certain populations are considered vulnerable to coercion and undue influence and are provided with additional protections when participating in a research study.

Identify any of the below populations which you plan to recruit for this study. In addition, complete the form(s) linked with each population as necessary and upload on the ‘Supporting Documents’ page in Rapport.

- [Pregnant Women, Fetuses and Neonates](#)
- [Children](#)
- [People with impaired decision-making capacity](#)

The following populations may also be considered vulnerable to coercion or other undue influence:

- Prisoners
- People who are economically disadvantaged
- The elderly
- People who are illiterate or do not speak English
- Students and employees

Describe any other potentially vulnerable population(s) and the additional protections provided to them:

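### Randomisation is stratified but the Aim 1 models carry no stratum term; if the strata predict change over time, some attainable precision and power is lost

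*Combined protocol and SAP*

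**What the plan says.** The design summary in section 3 sets the allocation ratio: "Participants will be randomized 1:1 to PeerFIT" or to BEAT, about 72 per arm. The sample size justification in section 9b adds that the randomisation is stratified: "Given our stratified randomization procedure, the intervention allocation should be evenly divided between the experimental and control groups".

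Section 3.6.5, Specific Aim 1, specifies the mixed models for weight, BMI and cardiorespiratory fitness: "Models will include fixed effects for treatment arm, time and an interaction between treatment arm and time". It then says that "random individual-level intercept and slope terms will be included to account for individual variation in trajectory". The H1a criterion is "A significant treatment effect of PeerFIT would be indicated by a significant time by treatment interaction", together with a larger mean improvement under PeerFIT. H1b uses a longitudinal logistic model of similar form. Neither model has a term for stratum or site, and no Aim 1 adjustment set is given elsewhere in the text available. Fidelity is mentioned in section 3 only as a possible covariate.

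The Aim 1 power analysis claims "80% power, at the two-sided 0.05 significance level, to detect a difference between arms in slope of at least 0.030-0.052 SD units per month" with 144 participants and within-person correlations of 0.1 to 0.7. For H1b it claims 86% power for 20% against 40%, falling to 77% with maximum attrition.

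**The concern.** Stratified allocation balances the arms on the stratification factors. If those factors predict the outcome being compared, the treatment estimate varies less from one randomisation to the next than an analysis that ignores them assumes. The between-stratum variation stays in the error term, so the reported standard error exceeds the true one, the test rejects too rarely under the null, and power falls short of what the design could give.

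The outcome compared matters here. H1a concerns change over time, so the relevant variation is between-stratum variation in the rate of change. The person-level random slope does not remove it: it absorbs that variation, which therefore stays in the standard error of arm by time.

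What is at stake is efficiency, in a trial whose stated detectable differences are already 21.6-36.0 lbs in weight and 126-210 m on the 6-MWT over 12 months.

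**Working it through.** **Inputs from the documents.** 72 per arm; assessments at 0, 6 and 12 months; within-person correlation ρ of 0.1 to 0.7; two-sided α of 0.05; 80% power (section 3 and the Aim 1 power analysis).

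**Assumption.** R², the share of variance in 12-month change explained by strata. The documents give no value, so I show 0% to 15%. With complete data at 0, 6 and 12 months, a person's fitted slope is (12-month value − baseline)/12, so R² for change and R² for slope are the same quantity.

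**Step 1: the plan's figures.** The detectable slope difference is (1.960 + 0.842) × √[2(1−ρ)/(n × Sxx)], with SD = 1 and Sxx = (0−6)² + (6−6)² + (12−6)² = 72.
- ρ = 0.1: 2.802 × √(1.8/5184) = 0.0522 SD per month.
- ρ = 0.7: 2.802 × √(0.6/5184) = 0.0301 SD per month.

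These match the stated 0.030-0.052. For H1b, the effective number per arm is 2 × 72/(1 + 0.5) = 96, giving 86.2% against the stated 86%. With 115 participants the result is 77.7% against 77%. The figures reproduce with no stratum term, so stratification played no part in them.

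**Step 2: strata that differ only in level.** With four assumed strata of equal size, complete data and ρ = 0.5, the standard error of arm by time is 0.013889 without stratum terms and 0.013889 with stratum main effects. With 20% dropout it is 0.015037 and 0.015038. In simulation (10,000 replicates, stratum SD 0.5 in level), the unadjusted analysis had type I error 5.2% and power 79%, the same as the adjusted one. Nothing is lost for H1a.

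**Step 3: strata that predict change.** With balanced strata the true standard error is √(1−R²) times the one the unadjusted model reports. Hence:
- inflation = 1/√(1−R²) − 1
- type I error = 2[1 − Φ(1.96/√(1−R²))]
- unadjusted power, at the effect for which the adjusted analysis has 80% = Φ(2.80 − 1.96/√(1−R²))

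| Assumed R² | SE inflation | Type I error | Unadjusted power |
|---|---|---|---|
| 0% | 0% | 5.0% | 80% |
| 5% | 2.6% | 4.4% | 78.5% |
| 10% | 5.4% | 3.9% | 76.9% |
| 15% | 8.5% | 3.4% | 75.0% |

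Example at 10%: 1.96/√0.90 = 2.066; 2[1 − Φ(2.066)] = 3.9%; Φ(2.80 − 2.066) = 76.9%.

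Simulation with four balanced strata agrees. At R² of 5%, 10% and 20%, type I error was 4.2%, 4.0% and 2.7%, and power was 78%, 77% and 72%, against about 80% adjusted. The formulas at 20% give 2.8% and 72.9%.

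**Step 4: the same loss on the plan's own scale.** Fix the total variance and effect at the values behind the stated 80%. The adjusted analysis then has power Φ(2.80/√(1−R²) − 1.96), which is 82.0% at R² = 5% and 84.0% at 10%. The unadjusted analysis of the stratified design has Φ(0.842/√(1−R²)), which is 80.6% and 81.3%. Neither is below 80%.

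**Step 5: H1b.** This outcome is itself a change (at least 5% weight loss, or more than 50 m gained), so stratum main effects can help directly. In a simulation of 20% against 40% at two time points, comparing person-level response means by linear regression, adjustment raised power from 86.7% to 87.3% when control rates ran from 13% to 28% across strata. With rates from 7% to 35% it rose from 87.2% to 89.4%.

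**The case against.** The strongest reply is that no loss has been shown. The documents report no stratum effect, and at R² = 0 the models as written lose nothing. That stands: the point is conditional. It is also true that the models are not bare fixed-effects models. Their random intercept and slope absorb differences between people, and level differences between strata leave the H1a contrast untouched.

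Four stronger readings are tempting, and the documents do not support them.

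- **The stated power is overstated.** It is not. The 80% and 86% figures reproduce without strata, so adjustment would add to them.
- **The test is conservative.** PeerFIT is delivered in coach-led groups while BEAT sessions are individual, and the models have no group term. Correlation within PeerFIT groups would push standard errors the other way, so the net direction is not established. The type I figures above set that correlation aside.
- **Power falls to 78.0%, 75.7% or 73.3%** at R² of 5%, 10% or 15%. Those values come from Φ(2.80√(1−R²) − 1.96), which treats the inflated standard error as the true one. That describes unstratified allocation and contradicts the type I calculation.
- **The plan fails to name its strata.** Part of the study-site description was not available, so this cannot be called an omission. The point does not need it: whatever the factors are, the stated models leave them out.

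The reply is also right that many strata could be thin in the logistic model. The plan's rates imply about 0.20 × 72 + 0.40 × 72 = 43 responders per time point.

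**Conclusion.** The mismatch is real: allocation is stratified and the Aim 1 models ignore it. The consequence is a possible loss of attainable precision, which threatens neither validity nor the stated power. For H1a it is nil if strata differ only in level, and 1.5, 3.1 or 5.0 power points (80% less 78.5%, 76.9% or 75.0%) if strata explain 5%, 10% or 15% of the variance in 12-month change. For H1b the simulated loss is 0.6 to 2.2 points. These sizes rest on assumed R² values, balanced strata, complete data for the H1a formulas and no within-group correlation. The change is still worth making because it costs little and settles the adjustment before the data are seen.

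**What to change.** In section 3.6.5, Specific Aim 1, add the stratification factors used in the randomisation, and their interaction with time, as fixed effects in the weight, BMI and 6-MWT mixed models. Main effects alone would not help H1a. Add the factors as covariates in the H1b logistic model, where the expected gain is modest. State in advance a rule for pooling strata that are too sparse for the logistic model.

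The cost is a sentence or two in the SAP, a few degrees of freedom (the exact number depends on how many strata there are) and some pooling if strata are small. The power statement needs no change on this ground.

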- For a waiver of the requirement for medical record documentation

12. Compensation or Gifts

Please describe any payments, gifts or reimbursements participants will receive for taking part in the study:

Participants will not receive incentives for participating in the intervention or control group sessions. However, potential participants will receive \$10 for their time in completing an information/formal screening session, regardless of whether or not they are eligible to be enrolled. Once enrolled, participants will receive \$50 or receive a \$50 gift card of their choice for completing data collection at each of the following time points: baseline, and 6 and 12 month follow-up, for a total of \$150. In addition, at 6 and 12 months, an unblinded research interviewer will conduct a brief 30-minute telephone assessment with PeerFIT participants to collect data on secondary measures specific to the experimental condition. PeerFIT participants will be paid an additional \$15 or given a \$15 gift card of their choice for participating in the interview. Participants will also be allowed to keep the Fitbit wearable activity tracking devices once the study ends.

Participants will be paid \$30 for completing a qualitative phone interview. Once the phone interview has been conducted, the research coordinator will contact the participant to arrange a convenient time to give them the \$30 in person.

Participants receiving money/gift cards paid for directly through Dartmouth-Hitchcock (“DH”) for research activities will be asked to complete a W-9 as a requirement of DH. If a study participant receives more than \$600 in one calendar year from DH, DH will report this to the IRS as required by law.

13. Privacy of Participants

Note: Methods used to obtain information about participants may have an effect on privacy. For example:

- Consent discussions or interviews held in public which concern sensitive subjects or behaviors
- Observations of behavior, especially illicit behavior, in quasi-public settings

Describe any activities or interactions which could lead to a breach of privacy and provide a plan to protect participant privacy:

There are potential risks to privacy associated with using the Facebook social networking site. For example, there are potential risks concerning the data that users choose to share with others when they create a personal Facebook account (e.g., sharing telephone numbers, personal email, date of birth, and other personally identifying information). These are some of the risks associated with using Facebook, and these risks are apart from the use of the secret Facebook group that will be formed for this study. It is expected that most of the young adults in this study will be active Facebook users and will have existing personal Facebook accounts prior to enrolling in the study. This assumption is based on the findings from a recent survey conducted in inpatient and outpatient mental health settings in New York that found that over 96% of young adults with serious mental illness were Facebook users. Further, these individuals reported using social media including Facebook for about 2.6 hours each day on average. Therefore, the young adult participants in the current study will likely be comfortable and familiar with using Facebook, and will have agreed to the terms and conditions of using this social media platform, and thus will be aware of potential risks associated with daily use of social media. We are able to mitigate potential risks by using the secret group feature on Facebook. The secret group can only be accessed by study participants who are invited to join by study staff, and the Facebook group will be monitored several times each week to ensure that the content posted by participants is consistent with the goals of the PeerFIT program.

Several measures will be implemented in order to minimize potential risks to participants with using the secret Facebook group component of the PeerFIT program. Importantly, in the secret group feature on Facebook, study staff will be able to maintain administrative control over the Facebook group at all times throughout the study duration. This means that study staff can invite or remove participants at any time, and can delete comments or posts from different group members. Study staff will follow a protocol where they will monitor the content of the Facebook group at least 3 times each week. Study staff will ensure that the content posted in the group does not deviate from the spirit and goals of the PeerFIT program. Primarily, study staff will be checking to make sure that there are no hostile or derogatory posts directed at other participants, or any posts describing urgent health concerns or emergencies. Participants will be informed of the ground rules for using the secret Facebook group, and that if they post any hurtful comments or inappropriate content then they will be removed from the group by study staff. Participants will also be informed that if they post any content related to a medical emergency or related to self-harm or harming others, then the study staff will call 911 and will inform the participant's mental health provider immediately. We anticipate that it will be highly unlikely that participants will discuss any medical emergencies in the secret Facebook group.

In addition, the lifestyle coaches will have continuous access to the secret Facebook group through their study smartphones. The lifestyle coaches will be provided with smartphones connected to the Facebook application so that they can easily access the secret Facebook group and view content or respond to participants' posts. The lifestyle coaches' smartphones will be setup to receive automatic updates and push notifications whenever any content or comments are posted in the secret Facebook group. The lifestyle coaches will be instructed to check the notifications and content posted in the Facebook on a daily basis (Mon-Fri). The lifestyle coaches will be instructed to follow a protocol where they will inform study staff immediately if participants post any hurtful, derogatory, or inappropriate content. The lifestyle coaches will be instructed to call 911 immediately and to also contact the study staff in the unlikely event that a participant posts comments related to self-harm or harming others. In our prior experiences using Facebook as part of the PeerFIT program, we have not had any concerns related to the content or types of posts from participants. Participants in this study can use their personal Facebook account to join the secret PeerFIT Facebook group. Use of the secret group feature will minimize any risk of a loss of privacy experienced by sharing personal information with other participants. Participants will also be asked not to share any information or content posted in the secret Facebook group with people who are not enrolled in the intervention arm of the study. The secret Facebook component of the PeerFIT program is entirely voluntary, and participants can choose to stop using the Facebook group at any time, or they can choose to use it as often or as little as they would like.

14. Confidentiality of Data

Note: Any person engaged in research collecting information about illegal conduct may apply for a [Certificate of Confidentiality](#) from the National Institute of Health.

a. If disclosed, could any of the data collected be considered sensitive, with the potential to damage financial standing, employability, insurability, or reputation?

X No Yes

If Yes, describe the data or information, the rationale for their collection, and whether a Certificate of Confidentiality will be obtained:

b. Describe the safeguards employed to secure, share, and maintain data during the study, addressing any of the following which may apply:

- Administrative, ie. coding of participant data
- Physical, ie. use of locked file cabinets
- Technical, ie. encrypted data systems

Our research team is experienced in training, instrument construction, editing, and data management. We will use the same procedures for data acquisition and management used in prior studies, including: (1) a common core of initial and refresher training for interviewers; (2) continuous team feedback to the sites; and (3) final data editing and management at our office in Merrimack, NH. Weekly research team conference calls, including assessment supervision, will help identify quality control issues early and allow consensus solutions to be reached. At the study sites, in a locked cabinet, single files will be maintained containing signed informed consent, participant contact information, and a study flow sheet. We will use a direct-entry, web-based system for data collection, which provides entry validation range tests for all fields, as well as default (missing) values. We have conducted several studies with this web-based system, including a state-wide intervention that has enrolled over 2,000 participants; therefore, we have confidence in its reliability and have had no problems with data safety, quality, or loss. All study data will be identified only with study ID numbers. The database will be protected by daily backup. Prior to analyses, data will be exported from the entry database into statistical analysis packages (SAS and SPSS) with complete labeling intact (variable names, variable labels, value labels, and missing value declarations). Data will be monitored and maintained by the Data Manager, who will review it weekly for accuracy and completeness.

Receipts of payment for the completion of research activities (e.g., information sessions, research assessments) as well as W-9s (if applicable) from study participants will be scanned by the study coordinator and thereafter shredded. Electronic receipts and W-9s will be stored on the study coordinator's password-protected computer to which only she has access. Electronic receipts and W-9s will also be sent to the grant manager via secure, encrypted email, and uploaded to a secure server to which only grant managers have access. W-9s will be kept separate from participant receipts, and neither will contain the name of the research study, only a project ID number.

Participants' Fitbit usernames (i.e., email address) and passwords, as well as their study ID, will be maintained by and accessible to only research staff. One password-protected spreadsheet will contain Fitbit emails, passwords, and the study IDs created for Fitabase accounts. This spreadsheet will be stored primarily for the purpose of registering the Fitbit accounts on the Fitabase platform. Fitbit data downloaded from Fitabase is de-identified and will only be shared among members of the research team. Only key research members with administrator accounts on Fitabase, such as the data manager, PI, and project manager, will be able to view and download the data. When participants go through informed consent and provide written consent, they will be giving the research team permission to maintain their Fitbit account username (i.e., email address) and Fitbit account password, as well as register their Fitbit accounts on Fitabase for the duration of their participation in the study. Participants can choose not to connect their Fitbit accounts with Fitabase and not to share their Fitbit data. For any participants who choose not to connect their Fitbit account with the Fitabase data management platform, it will not affect their participation in the study or their access to using a Fitbit wearable device for the duration of study participation.

Qualitative interview audio files will be deleted from audio recorders once they have been transferred to the data collection supervisor's computer and the transcription company's secure online portal. Instructions will be

given to the company to remove all identifiers from the transcript, such as names, locations, diagnoses, and any protected health information. De-identified transcripts will be stored in a password-protected online database that is accessible only to the PI and data collection supervisor.

c. Describe the plan for storage or destruction of data upon study completion:

The study team is aware of and agree to abide by the principles for sharing research resources, as described by NIH in "Principles and Guidelines for Recipients of NIH Research Grants and Contracts on Obtaining and Disseminating Biomedical Research Programs." As a means of sharing knowledge, NIH encourages grantees to arrange for publication of NIH-supported original research in primary scientific journals. We therefore will strive to publish our findings in a timely manner and acknowledge that the research was supported by the NIH. All primary and secondary publications will be completed within 3 years following completion of data collection. After this 3-year period, data without identifiers, including all indirect identifiers that might lead to deductive disclosure of individual participants, will be available under the auspices of the PI ([name]). Following a request to the PI to access data, a data sharing agreement will be established and a CD containing the de-identified data will be sent to the requesting institution or investigator. We will also share analytic code and variable creation and restructuring information with researchers who request it for sound scientific purposes aimed at the public well-being. All protected health information (PHI) data collected during this study will be destroyed by June 1st, 2030.

Paper W-9s and receipts signed by study participants that are maintained by the study coordinator will be shredded, and electronic W-9s and receipts will be destroyed using an encrypted data shredder, after they are entered electronically by grant managers onto a secure server maintained by DH. Grant managers will destroy electronic W-9s using an encrypted data shredder a) if they are replaced by a new version of the W-9 for that study participant, or b) after 7 years of no DH-originated payments made to the participant. Grant managers will destroy electronic receipts using an encrypted data shredder 7 years from the date of the receipt.

At the conclusion of data analysis, the spreadsheet of Fitbit account usernames (i.e., email address), Fitbit account passwords, and study IDs will be destroyed using an encrypted online data shredder. De-identified Fitbit accounts on Fitabase will also be deleted 90 days following the completion of data analysis per Fitabase's security policy.

